WHO	Target Population	
10 – 17 year olds who present at hospital having experienced or been impacted by: violence, assault or a risk of violence, whether weapon or non-weapon related, domestic or sexual violence, sexual or criminal exploitation.
 
Referrals made by (1) hospital staff member or (2) Redthread identifying an eligible CYP when reviewing the hospital systems
 
Eligibility criteria:
 
 1. Weapon-related injury (with the intention to do serious harm) 2. Concerns that incidents or individuals may be gang affiliated / have been exposed to or experienced violence/abuse 3. Concerns that an individual is at risk of further harm or abuse 4. A victim or perpetrator of a serious assault (with the intention to do serious harm) 5. Concerns or disclosures of domestic violence, sexual violence, including historic sexual violence/abuse 6. Concerns or disclosures of (Child) Sexual Exploitation or (Child) Criminal Exploitation. 
Planned Scale: approximately 350 CYP referred through 2022 with around 150 engaged in a longer term programme across three locations, Queen Elizabeth Hospital MTC (Birmingham), Birmingham Children’s Hospital MTC, Queen Elizabeth Hospital LTU (Woolwich, London) and St Mary’s Hospital MTC (Paddington, London).

HOW	Intervention Activities	
Hospital initiated Violence Intervention Programme delivered by Redthread workers that aims to contact CYP at a “reachable” moment. Following a referral Redthread workers will approach the CYP to seek consent to work with them and for their data to be stored and shared.
 
Short term crisis support - can include safety planning, emotional support, help with understanding medical treatment, attending relevant medical appointments, friends and family liaison, advocacy and signposting to statutory and community agencies, obtaining food vouchers/ clothing/ phone credit, safe travel after discharge, emergency accommodation.
 
Longer term (full programme of work) engagement - risk and needs assessment and joint action plan agreed. Plan can include: making safeguarding referrals as necessary, support navigating statutory systems (including CJS, welfare), casework around healthy relationships/ managing difficult emotions, support to (re)engage in education, securing alternative accommodation, accessing mental health or substance misuse support, accessing financial support and welfare

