	Participation What outputs must be achieved for the short term outcomes to be achieved.	10 – 17 year olds who present at hospital having experienced or been impacted by: violence, assault or a risk of violence, whether weapon or non-weapon related, domestic or sexual violence, sexual or criminal exploitation. Referrals made by (1) hospital staff member or (2) Redthread identifying an eligible CYP when reviewing the hospital systems Planned Scale: approximately 350 CYP referred through 2022 with around 150 engaged in a longer term programme across four locations, Queen Elizabeth Hospital MTC (Birmingham), Birmingham Children’s Hospital (MTC), Queen Elizabeth Hospital LTU (Woolwich, London) and St Marys MTC (Paddington, London).
OUTCOMES	Short Term Outcomes	
 • CYP understands their diagnosis/health plan • CYP feel safer • CYP offered appropriate safeguarding support • CYP better able to attend appointments, negotiate services and access support • CYP makes own appointments/plans for specialist ongoing support • CYP experiences successful engagement with specialist services themselves • CYP has onward plan for appropriate services
	Medium Term Outcomes	
 • CYP gains greater independence (e.g. makes own plans, appointments) • Improved wellbeing, self-esteem, and confidence
	Long Term Outcomes	
 • No readmission to hospital for violence-related incidents for 12 months • Reduced risk of future harm to self and others • Reduced mortality

Underpinning Aspects

ASSUMPTIONS	EXTERNAL FACTORS
Redthread can expect to receive referrals in from partner agencies listed above.	Availability of specialist services for Redthread staff to refer on to and thresholds of these organisations.
Eligibility criteria is appropriately applied.	

Research questions and/or objectives

The overarching research question is do CYP who engage with longer term support from RT have a reduced incidence of hospital re-admission for violent injury?

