The primary objective of our proposed evaluation is to provide a robust understanding of whether the RT programme targeted at CYP experiencing violence or at risk of abuse/exploitation leads to a reduction in violence/abuse related hospital readmissions in the subsequent one-year period. We aim to undertake a 1) process/implementation evaluation to assess how well the programme is being delivered and differences between delivery locations and an 2) impact evaluation to assess whether the RT programme leads to a reduction in violence/abuse related hospital admissions and other metrics.

Success criteria and/or targets

As agreed upon with YEF and RT, this project will run in two parts. The first element relates to the successful completion of a pilot phase lasting one year. This pilot will form the first part of an efficacy study, and the data gathered may contribute to the final analyses. Set progression criteria will determine whether the pilot proceeds to the efficacy study. The agreed progression criteria include:

1. Project implementation
 - a. UoB and RT are able to make a decision on the use of the SDQ/SRDS – based on RT run pilot (August 2022) and use within the pilot study (if the tools are used).
 - b. Intervention aligns with the ToC; if there is misalignment it will be necessary to re-visit the ToC, there is in general no need to stop the intervention but rather understand why the two diverge.
 - c. 75% of actions in an agreed action plan with CYP were implemented in a collaborative process involving staff and children; if this falls below 60% (Yellow), we need to discuss why this divergence is occurring and if it reaches 50% (Red) we will refer to YEF.
 - d. Personnel records show all youth workers received adequate supervision and support; this will be reviewed by UoB team and significant divergence will be reviewed with RT and YEF.

2. Recruitment and retention
 - a. Recruitment on to the intervention and into the control group is at least 60% of planned numbers within the pilot period. Anything below that is cause for concern (Yellow) with a need to pause (Red) if the response is below 40%.
 - b. CYP referred to and accepted on to the Redthread programme meet the eligibility criteria (referral form). We would expect the majority of CYP Redthread work with to meet these criteria, anything below 90% would prompt a need to discuss with Redthread.

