 - c. Redthread are able to retain CYP in support within the intervention to work through the action plan. At least 60% of planned numbers within the pilot period should be retained for a sufficient

period to complete this work. Anything below that is cause for concern (Yellow) with a need to pause (Red) if the response is below 40%.

3. Measurement
 - a. Hospital admission records (primary outcome)
 - b. Mortality data (secondary outcome)

Follow up data collection will continue for 1 year after the intervention.

It will be important to see how easily data can be matched between NHS and RT records. Not being able to match at least 80% of referrals is cause for concern and needs to be discussed (Amber), anything below a 60% match is serious cause for concern (Red) and may require us to revisit this method of capturing data.

Some key data issues such as incomplete/missing data or noncompliance or higher attrition rates than expected need to be considered. A certain level of missing data can be handled using statistical techniques, but quarterly audits should prevent this from becoming a serious problem.

These ratings relate to the feasibility of the methods of data collection of the pilot. Failure to meet success criteria, does not necessarily mean that the main evaluation should be abandoned, but will suggest that the proposed design or methods require revision. Provided the above are met or feasible alternatives can be found, we will recommend that we proceed to an efficacy trial, which will be completed via a separate ethics application. YEF will then reflect on the evidence the evaluation provides before a decision is made about the transition to the efficacy study.

The progression criteria will remain under review with more specific suggestions made as the evaluation proceeds (e.g. when it is clearer what a realistic proportion of completions of the SDQ might be possible with this cohort). Following the successful completion of this first year then we will focus on developing success criteria for the two-year efficacy study.

Methods

Study design

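### Retention criterion 2c is scored against planned numbers, not against the young people who started, so it mixes intake with retention and can rate adequate retention as Red

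*Protocol*

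**What the plan says.** All of this is in the protocol, mainly under *Success criteria and/or targets*.

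- **2a, recruitment:** "Recruitment on to the intervention and into the control group is at least 60% of planned numbers within the pilot period". Below 60% is Yellow and below 40% is Red, with a need to pause.
- **2c, purpose:** "Redthread are able to retain CYP in support within the intervention to work through the action plan".
- **2c, threshold:** "At least 60% of planned numbers within the pilot period should be retained" long enough to finish that work. The limits are those of 2a: "Anything below that is cause for concern (Yellow) with a need to pause (Red) if the response is below 40" per cent.
- **Planned scale (*Logic Model*):** "approximately 350 CYP referred through 2022 with around 150 engaged in a longer term programme across four locations". Neither 2a nor 2c says which of the two figures it uses.
- **Where action plans arise (*Theory of Change*, intervention activities):** "Longer term (full programme of work) engagement - risk and needs assessment and joint action plan agreed". This makes about 150 the natural base for 2c.
- **1c, implementation of agreed actions:** the target is 75%, but "if this falls below 60% (Yellow), we need to discuss why this divergence is occurring and if it reaches 50% (Red") the matter goes to the funder.

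The section says that the criteria decide whether the pilot moves on to the efficacy study. It also says that a missed criterion points to revising the design or methods and need not end the evaluation, and that the criteria remain under review.

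**The concern.** A retention criterion should ask what share of those who entered support stayed to the end of the planned work. Criterion 2c says that this is its purpose, and then divides by a planning figure that has nothing to do with how many entered. The other percentage criteria in the section with a natural cohort use that cohort: 1c uses the actions in agreed plans, 2b uses CYP referred and accepted, and the data-matching criterion uses referrals. Nowhere does the section give a retention threshold as a share of starters.

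Two different problems, slow intake and drop-out from support, therefore feed one rating, and slow intake is already rated under 2a. A pilot that recruits at the acceptable minimum and retains reasonably well could be told to pause on retention grounds. The *Sample size* section makes the distinction matter, because it treats power as adequate provided attrition among engaged CYP is not much above 50%. If programme drop-out contributes to that attrition, the pilot should report it undiluted by intake.

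**Working it through.** The protocol gives no derived figure to reproduce here; the thresholds are simply stated. The check is ratio arithmetic.

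**Inputs.** The green mark is 60% and the Red limit 40% of planned numbers, in both 2a and 2c. Planned number P = 150 (about 150 in the longer term programme, four sites together). **Assumption:** P is the same in 2a and 2c.

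**Identity.** retained / planned = (started / planned) × (retained / started).

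With intake f = started / planned, the retention needed among starters is:

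- for green on 2c: 0.60 / f
- to avoid Red on 2c: 0.40 / f

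For P = 150 the green mark is 0.60 × 150 = 90 and the Red limit is 0.40 × 150 = 60, for recruitment and retention alike.

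| Started | f | 2a rating | Retention needed for green on 2c | Retention below which 2c is Red |
|---|---|---|---|---|
| 75 | 0.50 | Yellow | 120% (impossible) | 80% |
| 90 | 0.60 | pass | 100% | 66.7% |
| 105 | 0.70 | pass | 85.7% | 57.1% |
| 120 | 0.80 | pass | 75% | 50% |
| 150 | 1.00 | pass | 60% | 40% |
| 180 | 1.20 | pass | 50% | 33.3% |
| 225 | 1.50 | pass | 40% | 26.7% |

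**At the 2a pass mark.** With 90 starters and 60% retained, 0.60 × 90 = 54 and 54 / 150 = 36%, which is Red. With 90% retained, 0.90 × 90 = 81 and 81 / 150 = 54%, which is Yellow.

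**When 2a is Yellow.** Fewer than 90 have started, so fewer than 90 can be retained, and 2c cannot be green at any retention.

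**Above plan.** 225 × 0.40 = 90, which passes. At exactly 100% of plan the rule asks for 60% retention, so the leniency begins only beyond that point.

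**Other readings of planned numbers.** If both criteria use 350, the percentages in the table do not change. If 2a uses 350 and 2c uses 150, the pass marks are 210 recruited and 90 retained, and 90 / 210 = 42.9%.

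**With starters as denominator.** 54 / 90 = 60%, which is green, and 60% retention has the same rating at every intake.

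**Criterion 1c.** The target is 75% and Yellow starts below 60%. Results from 60% to under 75% miss the target and carry no colour or action.

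**The case against.** **Planned numbers may differ between the two criteria.** Criterion 2a speaks of recruitment on to the intervention, which includes short-term crisis support, while action plans belong to the longer term programme. On a 350/150 reading the share required at the pass mark is 42.9% of recruits, not 100%. This stands as a limit on the 100% figure. It does not rescue the criterion: the text never states that reading, identical wording in one numbered block suggests one number, and 2c would still be a count against plan instead of a retention rate.

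**A count of completers against plan is a legitimate feasibility target.** It is, because power depends on yield. But 2c introduces itself as ability to retain. If yield is what is wanted, it should be named as such and rated beside retention.

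**Poor retention passing is remote.** This is largely right. The 40% example needs 225 starters from four sites, against roughly 300 a year across all 13 emergency departments: 225 / 300 = 75% of that volume. The practical weakness is over-strictness when intake is below plan.

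**The consequences are soft.** This also stands. Failure does not end the evaluation, the funder reflects before deciding, and 2a is reported alongside, so slow intake would be visible as a cause. A reader might infer that a Red on 2c stops the project. The protocol attaches a need to pause to Red, but its general text makes a missed criterion a reason to revise.

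**Conclusion.** The point holds. As written, 2c does not measure what it says it measures, and between the 2a pass mark and full planned intake it asks for more than 60% retention among starters. At 90 of about 150 started, green requires 100% and anything under 66.7% is Red, so 60% retention (54 CYP, 36% of plan) is rated as a reason to pause. When recruitment is Yellow, green on 2c is out of reach.

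These figures rest on planned numbers being the same in 2a and 2c. That is the natural reading, but it is not stated, and the missing definition is part of the defect. Two stronger inferences are not supported. The protocol does not demand complete retention in general: that applies only at the recruitment pass mark and on the same-number reading. Nor are these thresholds for a single hospital, since about 150 is the total for the four sites and no criterion is set per site.

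The practical weight is moderate: the rule can give a wrong rating, but the surrounding text leaves room to interpret and correct it. The gap in 1c is real and secondary.

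**What to change.** 1. **2c:** score it as CYP completing the action-plan work divided by CYP who started the longer term programme, keeping the 60% and 40% cut-offs. Count from the start of the programme and not from agreement of an action plan, because planning follows engagement and needs assessment and losses before it would otherwise disappear.
2. **2a:** state which planned number applies, about 350 referred or about 150 in the longer term programme.
3. **Yield:** if a minimum number of completers is wanted, add it as a separate count criterion. With starters as the denominator, 54 of 90 would be green on retention at 36% of plan, so a yield requirement has to be explicit if it matters.
4. **1c:** make the bands contiguous so that every result below 75% has a rating, with cut-offs agreed with the funder and the developer.

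The cost is wording to be agreed with the funder and the developer, and the criteria are already open to review. No new data are needed: *Process/implementation activities* already lists dosage and programme completion among the data to be collected.

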In such cases a clinical member of staff refers the CYP to the RT team. They can do this directly to the RT team when they are on shift and on site. Due to Redthread's position in the hospital, honorary NHS contracts, and safeguarding issues this can be done without consent from the CYP. When consent is sought, it is recorded in hospital systems. Referrals can be made face to face, via secure NHS email, phone or other local system e.g., referral button on hospital system, and will include the CYP's hospital number to allow RT to check hospital systems to establish eligibility. In cases where a RT team are not on site or on shift the clinician can complete a referral providing details of the CYP. It is standard practice at these sites for RT to also ask the clinician, to provide a safe number for them to use to contact the CYP, ask whether the CYP has a safe place to be discharged to and to make the usual referrals to hospital safeguarding as necessary. Most often the referral is made by a member of staff within the ED, but could also be a clinician elsewhere within the hospital who becomes concerned about a CYP. Referrals are managed and recorded by the Programme Coordinator and Team Leader of the RT team for each hospital site.

CYP can also be referred should they present in a different part or department of the hospital or if information about their risk factors transpire following their admission. They can also be identified by RT staff using information on hospital systems to ensure eligible CYP are not missed. The intervention is bespoke and led by the CYP's needs at that time. Once clinical needs are dealt with the intervention team continue building trust and a practical plan to help the CYP feel safe in preparation and following their discharge. The cases are closed once the CYP is safer and has engaged with a professional network that can support their longer-term goals, away from violence:

- For CYP who already have effective support of multiple existing agencies and/or a key professional, the intervention can be short-term and involves 'scaffolding' the reachable moment back into that CYP's professional network.

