RT have commissioned a number of evaluations of its programme within different hospital sites. A non-peer reviewed published evaluation undertaken on the programme in St Mary's hospital in London by NPC associates^{18,26} showed promising findings, regarding reducing hospital re-attendance rates for violence (a statistically significant fall compared to a pre-programme control group). YP using the service and professionals referring into it were supportive of the programme. However, there were limitations in the study design which affected the ability to draw a causal conclusion. Similarly, an evaluation of the programme in the Queen's Medical Centre undertaken by research staff there²⁷ showed lower re-attendance rates for YP who participated in the programme (both short term crisis support and full programme of work), compared to those YP who were eligible for the programme but did not engage with it. These results were found for re-attendance for any reason and specifically for violence or assault.

Mechanism for action and key outcomes

During the co-design phase we worked with RT and their partners (Dartington Service Design Lab) to undertake a Theory of Change exercise. This work involved key stakeholders and is on-going but a draft has been produced and is described below. The work has helped clarify what the different components of the programme are and the likely channels which have outcomes for CYP. In turn, this has enabled us to clarify the short-, medium- and long-term outcomes that are expected. As a result, during our sessions, we have considered the outcomes at length in consultation with YEF and RT both separately and as part of a co-design phase. Following the co-design stage, it became clear that the primary outcome should be reattendance coded for a violence or abuse related reason to hospital within 12 months from their initial discharge date. These data are available for both intervention and controls (see detail later) and we are confident that there will be sufficient power to distinguish the two groups. The secondary outcome will be mortality by any cause one year post contact with RT (this will draw on NHS data captured in the Summary Hospital level Mortality Indicator and other data which captures mortality beyond 30 days post discharge).

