2. Control group: This will consist of CYP (aged 10-17) who either were eligible for the intervention but did not take part (this will include those who could not be contacted by RT following a referral. It should not include those who refused to take part in the intervention) or taken from historic data prior to the introduction of the intervention in each site.

Theory of change:

The initial phase of the evaluation will be to refine the theory of change (ToC) for the programme with the RT senior team. The organisation Dartington Service Design Lab have been commissioned to undertake the ToC with RT. However, they were commissioned to undertake the ToC for the whole service and the programme we are evaluating is only part of the wider RT offer. Therefore, our initial activities will be to undertake 1-2 focus groups consisting of 5-10 individuals remotely of RT senior staff to clarify and finalise the ToC for this project. This will inform data collection, analysis, and interpretation. As the feasibility study progresses, we will continue to consult with RT, clinical colleagues and most importantly CYP eligible for the intervention, about the ToC and Logic model. This part of the study has been reviewed by the UoB ethics committee.

This will include discussions around:

1. Problem Identification

Describing the problem that the project is designed to address. The description of the problem should be based on an analysis of data and relevant information and should be rigorously checked for availability, accessibility, completeness, and accuracy.

2. Response/Resources

How does the intervention address cause of the identified problem? This will include:

- What are the causal links assumed between the project approach and the problem?
- How and why does/will the project approach address the problem?
- Are there parts of the problem the project approach does not address?
- How do any current approaches need modifying to address all aspects of the identified problem? This would include a discussion of the associated dosage (which varies from case to case) and mode of delivery.

3. Outputs

Describing what is expected to be produced as a result of the response. Outputs are not used to evaluate the success of the intervention (as outcomes are), rather they are the measurable elements of project approach and generally describe the amount of activity expected or delivered.

4. Outcomes

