- Interviews / group interviews with clinical staff at the hospital sites who refer into RT. Topics would cover their use and opinions of the RT service, the alternatives to RT locally and the effect it has and ways it could be improved. We aim to conduct one focus group (consisting of 4-6 individuals) per site and the staff are likely to consist of ED doctors, nursing and professional services staff. We would expect the team leads at Redthread to initially approach referral staff to gain consent for their contact details to be passed to the research team. Potential interviewees will be given Participant Information Sheets prior to UoB staff consenting them into the study. We expect each interview/focus group to last between 30-60 minutes and will be in person (in their chosen location) or on Zoom/Teams if Covid restrictions again come into place.

Inclusion/exclusion criteria:

Participant Group	Inclusion Criteria	Exclusion Criteria
Children and Young People (CYP)	Capacity to consent to the Redthread programme.	
	CYP aged (10-17) who have undergone the Redthread programme in any of the four participating sites. Redthread eligibility criteria: 10-17 year olds who have presented at hospital having experienced or been impacted by: violence, assault or a risk of violence, whether weapon, or non-weapon related, domestic or sexual violence sexual or criminal exploitation.	
Controls (PSM)	CYP (aged 10-17) who were eligible for the intervention but did not take part; or eligible CYP taken from historic data prior to the introduction of the programme in each site. This will include those who could not be contacted by Redthread following a referral.	CYP who were offered but refused the Redthread programme.
Parents/carers (for CYP under 16 years old)	Capacity to consent to their CYP taking part in the Redthread programme. Where appropriate we will provide the PIS in alternative languages.	None.
Redthread staff	All programme managers and a representative of each job role within the team across the four hospital sites.	None.
Community Partnership staff NHS Staff	Consenting non-hospital personnel who work with Redthread in joint case work, and representatives of organisations receiving onwards referrals.	None.
	Consenting NHS clinicians and other staff who refer CYP to the Redthread teams.	None.

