As highlighted above, we aim to undertake a QED with PSM to ascertain impact. The PSM study will consist of collecting data from the treatment group (from the four RT hospitals) and then, with the support of the relevant health informatics teams at the sites, identify a suitable group of controls who have not used the service from at least one of the existing sites (but who have not refused that service as including those who refuse service would create a selection bias). This could be drawn from contemporaneous or historical data, depending on the processes RT uses to gather referrals; for example, whether there would be a group of suitable CYP not approached by RT. This data will be provided to us without any personal identifying information. The groups will then be propensity score matched to identify the most suitably similar controls based on a variety of demographic and clinical data that we have in both the hospital record and RT dataset. This is likely to include age, gender, severity and nature of their injury, or level of risk to the CYP based on RT's eligibility criteria (weapon-related injury or a serious assault with the intention to do serious harm; concerns that incidents or individuals may be gang affiliated or have been exposed to or experienced violence/abuse; concerns that an individual is at risk of further harm or abuse; concerns or disclosures of domestic abuse, sexual violence, including historic sexual violence/abuse; concerns of (Child) Sexual Exploitation or (Child) criminal exploitation). These variables are chosen because they are related to both the treatment and the outcome and are common in the literature (see e.g. Shibru et al., 2007).

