We foresee challenges in the collection of hospital data from the intervention and control sites. However, we have experience in working with NHS trust site directors, health informatics teams, and emergency departments and believe that these challenges are ones that we can address. We have discussed with RT who will provide us with the treatment data and will support our team in the extraction of pseudo anonymised control data supported by the relevant health informatics teams who will assign case IDs to those in the control group.

We will use this phase to explore whether it will be possible to collect control data on current cases, who do not receive support from RT, or whether it will need to be constructed from historic data. Discussions of RT practice during the co-design phase highlighted that RT staff in hospital sites do review hospital admissions to check for missed referrals and that they follow up referrals made when staff are not on duty. This risks contaminating any concurrent control group and reduces the pool of eligible CYP for such a control group.

During this phase we will complete a Template for Intervention Description and Replication (TIDieR) Checklist for the proposed control sample as we have done during the co-design phase for the intervention. This will include defining precisely what Business as Usual (BAU) consists of across sites. Mostly likely, this will be statutory safeguarding practices, although it may well be that this varies from one Trust to another and this will, of course, influence the effect size found in the intervention. The implementation study will aim to track both the intervention and assess what the comparison group receives.

Sample size

During the co-design phase we identified approximately 300 CYP (aged under 18 years) are engaged in a longer term programme annually across all 13 ED sites. Our sampling considerations have been informed by existing literature on the topic.^{3,17} Much of the existing literature to date has focussed on criminal justice outcomes with no comparable study examining the risk of re-hospitalisation.

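### Historic controls are bounded only by the programme's start date, so those discharged in the preceding 12 months have follow-up that runs into the programme period and may not be unexposed

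*Protocol*

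**What the plan says.** The Participants section (impact evaluation, control group) gives two sources of controls: eligible young people who did not take part, or people "taken from historic data prior to the introduction of the intervention in each site". The Controls row of the inclusion/exclusion table repeats the second source as "eligible CYP taken from historic data prior to the introduction of the programme in each site". The only date in either place is the introduction of the programme.

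The section on mechanism and key outcomes defines the primary outcome as "reattendance coded for a violence or abuse related reason to hospital within 12 months from their initial discharge date".

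Control group data collection asks the informatics teams to "identify a suitable group of controls who have not used the service from at least one of the existing sites", with no time limit on the condition about service use. It leaves the source open: "This could be drawn from contemporaneous or historical data, depending on the processes RT uses to gather referrals".

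On what happens once Redthread is on site, the Intervention section says of young people not yet referred: "They can also be identified by RT staff using information on hospital systems to ensure eligible CYP are not missed". Control quantitative data confirms that "RT staff in hospital sites do review hospital admissions to check for missed referrals". It treats this as a contamination risk for a concurrent control group and names historic data as the alternative.

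**The concern.** The historic option is the protocol's answer to contamination of concurrent controls. The rule as written dates the control's entry but not the end of the outcome window. A young person discharged shortly before launch is eligible, yet is then followed through months in which Redthread takes referrals and screens hospital systems at the same site. The contamination the historic option was chosen to avoid can return for these late controls.

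The condition that controls have not used the service does not settle the matter, because it has no time limit:

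- **Judged at index only.** A late control may be engaged by Redthread during follow-up, before any violence reattendance, and stays in the control group.
- **Applied through follow-up.** A late control whose violence reattendance leads to Redthread engagement is taken out of the control group because the outcome occurred. That is selection on the outcome, and it lowers the control event rate.

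If the programme works, the first lowers the control event rate; the second lowers it whether or not the programme works. Both shrink the apparent benefit.

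**Working it through.** **Inputs from the protocol.** Latest permitted index date: the day before introduction at the site (Participants; inclusion/exclusion table). Follow-up: 12 months, taken as 365 days, from discharge (Mechanism for action and key outcomes). Required gap between index and launch: none stated.

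**Inputs not in the protocol.** The look-back length W of the historic pool and the site launch dates. W is therefore assumed and shown as a range of 1 to 5 years, with discharges spread evenly over the pool.

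The protocol gives no overlap figure to reproduce. Its nearest calculated figure is 392 per group for d = 0.2 and 80% power. With a two-sided 5% level assumed, this comes to 392.4 before rounding, so it reproduces. It is used below only for scale.

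**Step 1: one control.** For discharge g days before launch, the share of follow-up after launch is max(0, (365 − g)/365).

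- g = 1: 364/365 = 99.7%
- g = 30: 335/365 = 91.8%
- g = 91: 274/365 = 75.1%
- g = 182.5: 182.5/365 = 50%
- g = 365 or more: 0%

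**Step 2: the whole pool.** For W of at least 1 year, the fraction of controls with any overlap is 1/W. Among those the average share is 50%, so the mean over all controls is 0.5/W.

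| Assumed pool W | Controls with any overlap | Of 392 controls | Mean share of follow-up after launch |
|---|---|---|---|
| 1 year | 100% | 392 | 50% |
| 2 years | 50% | 196 | 25% |
| 3 years | 33% | 131 | 17% |
| 5 years | 20% | 78 | 10% |

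**Step 3: from overlap to bias.** Overlap is opportunity for exposure, not exposure. There are two routes to bias:

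- *Exposure before the outcome.* This needs a contact that brings the control to Redthread's notice without itself being a violence or abuse reattendance, or pick-up through the review of hospital systems. The protocol has no figure for how often this happens.
- *Removal because of the outcome.* This needs the service-use condition to be applied beyond the index date. The protocol neither says so nor excludes it.

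**Step 4: with a cut-off.** If every historic control is discharged at least 365 days before launch at the site, Step 1 gives 0% overlap for all of them.

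**The case against.** The strongest case on the other side has four parts.

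1. **The wording may date the data, not the attendance.** The data collection table lists reattendance among the control data, so historic data from before introduction could mean that the outcome data are pre-programme too. The phrase does allow this. But both places use it to say who the controls are, so the natural reading dates their entry. On the other reading, late controls would have less than 12 months of outcome data unless a cut-off is applied. The same sentence is needed either way.

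2. **The source of controls is undecided, and the pilot will not support causal inference.** Both are true, and if only concurrent controls are used the point falls away. However, the Sample size section regards historic data as the more feasible way to get groups of similar size, and the success criteria section says pilot data may feed the final analysis.

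3. **A date cut-off is detail for the analysis plan.** Often so, but here the protocol itself states the eligibility rule, and an informatics team could extract on it as it stands.

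4. **Redthread entry after a violence reattendance cannot bias the outcome.** This stands as far as it goes: the yes/no outcome has already been recorded. A reader might infer that such entry in itself contaminates the comparison. It does not. Only exposure before the outcome, or removal of the control afterwards, does harm.

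**Conclusion.** The point holds in a limited form. The historic-control rule permits follow-up to overlap the programme period for anyone discharged in the 12 months before launch. Depending on the assumed pool length, 20% to 100% of controls would be affected, and 10% to 50% of control follow-up would fall after launch. These figures rest on even spread and on pools of 1 to 5 years; neither is stated in the protocol. The likely direction is towards no effect.

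Three stronger readings are not supported:

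- **That at most half of a control's follow-up can overlap.** Half is the average for an evenly spread one-year pool. For a single control the maximum is essentially all of it.
- **That historic controls in general are exposed.** Controls discharged 12 months or more before launch have no overlap at that site, and the others are only possibly exposed.
- **That the loss in the control event rate can be calculated.** One could take the protocol's 7.8% and its planned 150 engaged out of 350 referred, and drop engaged reattenders. For a one-year pool, 7.8 × 0.50 × 150/350 = 1.67 points, and (7.8 − 1.67)/(100 − 1.67) = 6.2%. For a two-year pool the same sum gives 7.0%. These are illustrations only. The 7.8% is a US figure that the protocol itself offers as an illustration. The 150/350 is longer-term engagement among those already referred, so using it assumes that every reattender is referred from the first day. The sum also assumes removal after the outcome, which the protocol does not prescribe.

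The size of the bias therefore remains unknown. It is worth correcting because it can be avoided before any data are extracted.

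**What to change.** In the Participants section and in the Controls row of the inclusion/exclusion table, require that a historic control's index discharge falls at least 12 months before the programme's start date at that site. The whole outcome window is then pre-programme there.

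In Control group data collection, state that the condition of not having used the service is judged at the index date and not by anything that happens during follow-up.

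The cost is one extraction rule for the informatics teams, plus the loss of the most recent pre-programme year. Controls are then somewhat further back in calendar time, which slightly widens any difference in background conditions between the groups. Censoring follow-up at launch would keep those controls, but it needs a time-to-event analysis and departs from the fixed 12-month outcome, so the cut-off is simpler.
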